1.5 Risk Benefit Assessment

Fezolinetant is currently being developed for the treatment of VMS associated with the menopause (MR-VMS).

Based on recent advances in science, as well as the clinical data derived from 2 phase 2 clinical studies in women with VMS associated with the menopause, there are positive reasons to believe that fezolinetant can be an effective treatment for MR-VMS and treatment-resistant VMS.

When given to normally cycling healthy women, fezolinetant is capable of altering the menstrual cycle and decreasing the circulating levels of E2, LH, progesterone (P4) and testosterone. Since this study aims to include menopausal women, these effects will be of less importance because of the physiological changes that happen in the climacterium (anovulation with loss of P4 and E2 production and consequently increase of LH/FSH).

In terms of hormonal changes, a mild to moderate decrease of the already elevated LH and FSH plasma levels is anticipated. There are no known risks associated with this decrease of the gonadotropins in menopausal women.

Treatment with fezolinetant can cause adverse effects or other symptoms. Adverse effects that can be expected are those AEs that presented in fezolinetant clinical studies in healthy male and female volunteers, as well as in menopausal women.

Details of the AE profile from the completed clinical studies are presented in [[Section 1.3 Fezolinetant Nonclinical and Clinical Data](#)].

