7.8 Analysis of Pharmacodynamics

Individual serum hormone concentration values and actual sampling times relative to study drug intake will be listed. Descriptive statistics (number of subjects, mean, SD, median, minimum and maximum) on the actual values and changes from baseline values will be summarized by assessment timepoint and by treatment arm. Pharmacodynamic data and efficacy data may be evaluated by a population pharmacodynamics or population pharmacokinetic/pharmacodynamic approach. All details of population analyses will be described in the SAP. When deemed necessary, data from this study may be combined with data from other studies.

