In general, summary statistics will be provided for all the safety parameters. Treatment comparisons will be performed for endometrial and bone density related endpoints. For AESI, the rate, odds ratio and their corresponding 95% exact confidence intervals will be presented, which will be constructed based on Santner-Snell approach. An ANCOVA model, with treatment and strata smoking status (current vs former/never) as factors, with baseline weight and baseline as covariates, will be used for single assessment continuous endpoints. Each following section will specify the analysis method appropriately.

The change and percentage reduction in serum concentrations of sex hormones and sex hormone-binding globulin (SHBG) from baseline to each analysis visit will be summarized.

For hormone related parameters, if the value is below the low limit of quantification, the value will be imputed as half of the LLOQ. In addition, the percentage of subjects who have BLOQ values at baseline who then have measurable post-baseline values will be summarized.

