6.7 Analysis of Pharmacodynamics

Serum concentrations of sex hormones [luteinizing hormone (LH), follicle-stimulating hormone (FSH), estradiol (E2), Testosterone Total/Free, Androstenedione, dehydroepiandrosterone (DHEA), Estrone] and sex hormone-binding globulin (SHBG) will be summarized using descriptive statistics (number of subjects, mean, SD, median, minimum and maximum) for each visit and time point and for change from the baseline to each postdose visit, if the data is available.

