6.10 Additional Conventions

6.10.1 Analysis Windows

Study Day for analysis windows will be calculated as date of visit/assessment – first dose date +1.

Study Day for the follow-up (FUD) phase will be calculated as date of visit/assessment – last dose date of study treatment (Date of EOT).

Except for adverse events, for the analysis window (weeks prior to the follow-up period), the last day is always 1 day after the last day of exposure to double-blind treatment.

The end of overall treatment is defined as the last day of treatment +1 and the follow-up period begins at last overall treatment + 2 days and onward (Follow-up Study Day 2).

The data summary by visits will be done following the analysis windows specified in the table below:

Analysis	Scheduled	Analysis Windows (day)				
Visits	Day in Protocol	a)	b)	c)	d)	e)
Baseline	Day 1	Last non-missin	ng value on or prio	or to day 1 (inclu	sive)	
Week 2	Day 15	2 to 22				
Week 4	Day 29	23 to 43	2 to 43	2 to 57		
Week 8	Day 57	44 to 71	44 to 71			
Week 12	Day 85	72 to 99	72 to 99	58 to 127	2 to 127	
Week 16	Day 113	100 to 127	100 to 127			
Week 20	Day 141	128 to 155	128 to 155			
Week 24	Day 169	156 to 183	156 to 183	128 to 267	128 to 267	
Week 28	Day 197	184 to 211	184 to 211			
Week 32	Day 225	212 to 239	212 to 239			
Week 36	Day 253	240 to 267	240 to 267			
Week 40	Day 281	268 to 295	268 to 295			
Week 44	Day 309	296 to 323	296 to 323			
Week 48	Day 337	324 to 351	324 to 351			
Week 52	Day 365	352 to 376	352 to 376	268 to 376	268 to 376	2 to 376
Follow-up	Day 386	Last treatment + 2 days and onwards				

a) Apply to Clinical laboratory and urinalysis

b) Apply to Vital signs

- c) Apply to Blood PD/PK sample, EQ-5D-5L, MENQoL
- d) Apply to C-SSRS
- e) Apply to 12-lead ECG

For TVU and DXA, the week 52 analysis window is day 2 to last treatment + 30 days. For endometrial biopsy, refer to Section 6.5.5 for analysis window.

As a general rule, if more than one observation exists within the analysis window, the observation closest to the scheduled visit day will be selected for that visit. If there are two observations that have the same distance from the scheduled day, the value that is after the scheduled day will be selected in the analysis. If more than one observation is made on the same day, an average value if continuous or the worst value if categorical will be included in the analysis.

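### Percentage reduction in sex hormones is computed with half-LLOQ substitution, baseline included, and crossings of the assay limit are counted in one direction only, so the within-arm summary is partly set by the substituted constant

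*SAP*

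**What the plan says.** SAP 6.5 plans two summaries of relative and absolute change: "The change and percentage reduction in serum concentrations of sex hormones and sex hormone-binding globulin (SHBG) from baseline to each analysis visit will be summarized". It then substitutes a constant for low hormone results: "if the value is below the low limit of quantification, the value will be imputed as half of the LLOQ". Nothing limits that rule to post-baseline values. The SAP clearly expects some baselines below the limit, because it adds one transition table: "the percentage of subjects who have BLOQ values at baseline who then have measurable post-baseline values will be summarized". Neither document specifies a count in the opposite direction, a log-scale summary, a censored-data method or a sensitivity analysis for the substitution.

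Other planned outputs bear on the point. SAP 6.7 gives n, mean, SD, median, minimum and maximum of the values and of the changes by visit. Protocol 7.8 adds that "Individual serum hormone concentration values and actual sampling times relative to study drug intake will be listed". SAP 6.5 presents safety results by arm, placebo included. Hormone change is an exploratory endpoint in Protocol 2.3.3 and SAP 5.3, and the SAP attaches no hypothesis test to it.

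**The concern.** A percentage change needs a real denominator. When baseline is a substituted constant, the result depends on that constant and on whether the later value happens to cross the assay limit. Hormones that are low after menopause, such as E2, are where this is likely to matter. Ordinary within-woman variation then produces recorded rises of 100% or more from below the limit, and recorded falls of 50% or more from just above it. Because only the upward crossings are counted, a reader of the tables sees one half of that noise as a count and the other half only inside an average.

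At stake is the readability of an exploratory hormone summary that a reader may set beside the endometrial and bone results. No primary or secondary conclusion depends on it.

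**Working it through.** **Inputs.** The substitution rule, the percentage summary and the one-way table come from SAP 6.5. The documents state no LLOQ, no expected share of values below it and no figure for this analysis, so there is nothing to reproduce. I write L for the LLOQ and assume one L per hormone throughout; Protocol 5.7.2 sends the samples to a central laboratory, which supports this. Percentage reduction = 100 × (1 − post/base), with any value below L set to L/2.

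**Algebra.**

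1. Below L at baseline and later: 100 × (1 − (L/2)/(L/2)) = 0%.
2. Below L at baseline, later kL with k ≥ 1: 100 × (1 − 2k) ≤ −100%, a rise of at least 100%. One rare exception arises from SAP 6.10.1: "If more than one observation is made on the same day, an average value if continuous" is used. A substituted value averaged with a value of L is 0.75L, which gives a rise of 100 × (0.75/0.5 − 1) = 50%.
3. Baseline bL with b ≥ 1, later below L: 100 × (1 − 1/(2b)), that is 50% at b = 1, 75% at b = 2, 90% at b = 5 and 95% at b = 10. The true reduction can lie anywhere from 100 × (1 − 1/b) to 100%, so at b = 1 from 0% to 100%.
4. With another constant cL, the smallest rise in step 2 is 100 × (1/c − 1): 100% for L/2, 41.4% for L/√2, 0% for L. Step 1 stays at 0% whatever the constant.

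**Illustration (all inputs assumed).** Lognormal hormone, between-woman log SD 0.6, within-woman log SD 0.3, simulated pairs; figures carry simulation error of about 0.1 to 0.2. A negative reduction is a rise.

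| Below L at baseline | Mean reduction, no effect | Mean reduction, true 20% fall | Difference (points) | Median reduction, true 20% fall |
|---|---|---|---|---|
| none | −9.4% | 12.5% | 12.5 + 9.4 = 21.9 | 20% |
| 30% | −14.7% | 8.9% | 8.9 + 14.7 = 23.6 | 5.6% |
| 50% | −13.6% | 6.7% | 6.7 + 13.6 = 20.3 | 0% |
| 70% | −10.1% | 4.4% | 4.4 + 10.1 = 14.5 | 0% |

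The first row shows that averaging percentage changes produces an apparent rise of 9.4% even with nothing below the limit. With no drug effect, the substitution adds 14.7 − 9.4 = 5.3, 13.6 − 9.4 = 4.2 and 10.1 − 9.4 = 0.7 points. At 50% below L and no effect, the women below L at baseline average a 34% rise; with a true 20% fall they still average a rise of about 15%.

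**Crossings.** With a true 20% fall in place of no effect, the planned count (below L to measurable) drops from 29.6% to 15.2%, from 20.5% to 9.6% and from 12.6% to 5.4% at 30%, 50% and 70% below L. The count that is not planned (measurable to below L) goes from about 20.5% to about 36% at 50%.

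**Alternatives on the same model.** A geometric mean ratio to baseline in all women, keeping L/2, is 1.00 with no effect at every share. For a true 0.80 it is about 0.83 at 50% and 0.88 at 70%. Restricting to women with a quantifiable baseline gives a spurious geometric reduction of about 12%, 18% and 24% with no effect at 30%, 50% and 70%, through regression to the mean.

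**Other assumptions.** With total log SD 0.5, within-woman correlation 0.7 and a true 30% fall, the median change is −30.7%, −22.7%, 0% and 0% at 10%, 30%, 50% and 70% below L. The geometric mean ratio in all women is 0.66, 0.68, 0.73 and 0.82 against a true 0.70, so it can also overshoot slightly when the share is low.

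**The case against.** The strongest reply is that the placebo arm shows the same artefact. On the illustration above, the between-arm difference in means is 23.6 and 20.3 points at 30% and 50% below the limit, against 21.9 with no limit; only at 70% does it shrink materially, to 14.5. Absolute changes, ranges and individual listings are also planned, so the missing count can be recovered. Endometrium and bone are assessed directly by biopsy, ultrasound and DXA. All of this stands, and it makes the point minor. It does not repair the within-arm mean, and the planned median does not help once it has gone to 0.

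Three stronger readings are tempting but unsupported:

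- A reader might infer that the half-LLOQ rule hides a true fall in women already below range. The assay limit does that: step 4 gives 0% for every constant. Falls from a measurable baseline do enter the percentage summary.
- A reader might infer that the one-way table cannot show suppression. It can, as fewer upward crossings on drug than on placebo.
- A reader might take Protocol 1.5, where "fezolinetant is capable of altering the menstrual cycle and decreasing the circulating levels of E2, LH, progesterone (P4) and testosterone", to mean that E2 and testosterone are expected to fall here. That sentence concerns normally cycling women, and the protocol goes on to give the effects less weight in menopausal women. What it anticipates in this population is a fall in LH and FSH from elevated levels, where values below the limit should be few.

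**Conclusion.** The point holds as a defect in the summary measure. Under SAP 6.5 a woman below the limit at baseline can show only 0% or a rise of at least 100% (apart from the same-day averaging case), and a drop below the limit is recorded as at least 50%. That much is algebra, given one LLOQ per hormone. The within-arm mean is therefore partly set by the constant and skewed towards a rise, and the median goes to 0 when about half or more are below the limit.

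The size rests on assumed variances and an unknown share below the limit. In the illustration, a mean reduction of 12.5% with no limit becomes 8.9%, 6.7% and 4.4% at shares of 30%, 50% and 70%, while the placebo contrast keeps much of its signal until the share is high. The concern is mainly with low-level hormones such as E2, and hardly with LH and FSH. Severity is minor, because the endpoint is exploratory and descriptive.

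**What to change.** In SAP 6.5 and 6.7:

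- Tabulate both directions, from below the limit to measurable and from measurable to below it, with the percent below the limit at each visit, by arm.
- Summarise relative change as a geometric mean ratio to baseline in all women, by arm and against placebo, with the number of substituted values shown. It can replace the arithmetic mean percentage reduction or stand beside it.
- Do not restrict the main summary to women with a quantifiable baseline, given the spurious reduction shown above. Use that subset only as a supplementary comparison against placebo.

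The cost is SAP wording and a little programming; no new data are needed. The geometric mean ratio is not a full remedy: it is still attenuated when the share below the limit is high, which is why the number substituted must be shown beside it.

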6.5.1 Adverse Events

Per protocol, a treatment emergent adverse event (TEAE) is defined as the AEs that occurred on or after first dose of study drug and 21 days after the last dose of study drug (when AE collection closes).

A study drug-related TEAE is defined as any TEAE with a causal relationship of YES by the investigator.

The sponsor has a list of events that they classify as "always serious" events. If an AE is reported that is considered by the sponsor to be an SAE per this classification as "always serious", the AE will be treated as an SAE in tables and listings, and flagged as 'always serious' in AE listings.

An overview table will include the following

- Number of TEAEs,
- Number and percentage of subjects with TEAEs,
- Number of drug related TEAEs,
- Number and percentage of subjects with causally drug related TEAEs,
- Number of serious TEAEs,

- Number and percentage of subjects with serious TEAEs,
- Number of serious drug related TEAEs,
- Number and percentage of subjects with serious drug related TEAEs,
- Number of TEAEs leading to permanent discontinuation of study drug,
- Number and percentage of subjects with TEAEs leading to permanent discontinuation of study drug, and
- Number of deaths.

In order to adjust for differences in subjects' durations and the potential differential dropout rates between the treatment groups, an overview table to report exposure adjusted incidence rate (per 100 subject-years) for the above AE categories will be summarized. The total subject-years of exposure is calculated as the sum over subjects of the total duration of exposure divided by 365.25:

$$\sum_{i} \frac{ld_i - fd_i + 1}{365.25},$$

where fd_i and ld_i denote the first dose date of study drug and the last dose date of study drug for subject *i*.

The number and percentage of subjects with TEAEs in the following AE categories will be summarized for each treatment group by system organ class (SOC), high level term (HLT) and preferred term (PT):

- TEAEs
- drug related TEAEs.

The number and percentage of subjects with TEAEs in the following AE categories will be summarized by SOC and PT:

- serious TEAEs,
- drug related serious TEAEs,
- TEAEs leading to permanent discontinuation of study drug,
- drug related TEAEs leading to permanent discontinuation of study drug,
- TEAEs that equal to or exceed a threshold of 5.0% in any treatment group (threshold is based on PT).
- TEAEs excluding serious adverse events that equal to or exceed a threshold of 5.0% in any treatment group.

The number and percentage of subjects with TEAEs, as classified by PT only, will be summarized for each treatment group.

The number of TEAEs and the number and percentage of subjects with TEAEs, as classified by SOC and PT will be summarized by severity and by relationship to study drug. In the subject count, if a subject has multiple TEAEs with the same SOC or PT, but with differing severity or relationship, then the subject will be counted once with the worst severity and highest degree of relationship. If severity or relationship is missing for all episodes of the event, the subject will be counted under missing severity or relationship. In the adverse event count, the adverse events will be presented in each category they were classified to. Drug related TEAEs will be presented in a similar way by severity only.

Among TEAEs, following adverse events of special interest (AESI) are defined:

- Adverse event of endometrial hyperplasia/cancer or disordered proliferative endometrium
- Adverse event of liver test elevations
- Adverse event of uterine bleeding
- Adverse event of thrombocytopenia
- Adverse event of bone fractures
- Adverse event of abuse liability
- Adverse event of depression
- Adverse event of wakefulness
- Adverse event of effect on memory

Search terms defining the AESIs will be pre-specified and documented. The number and percentage of subjects with AESIs as classified by PT will be separately summarized for each treatment group.

The number and percentage of subjects with TEAEs associated with COVID-19, as classified by PT, will be summarized for each treatment group, fezolinetant total and overall.

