- a. The screening visit is to occur on or within 35 days of randomization (day 1 [visit 2]). Subjects may be retested 1 time for assessments upon approval of the medical monitor. An extra 15 screening days are allowed for repeat biopsy, if necessary (days -50 to -1, including the screening visit [visit 1] assessments). The following assessments do not need to be repeated at the rescreen provided they still fall within the acceptable screening time window: TVU, DXA, endometrial biopsy, mammogram, ECG and Pap test (or equivalent cervical cytology). Subjects who screened for the 2693-CL-0301 or the 2693-CL-0302 study that did not meet the minimum requirement for frequency and severity of VMS prior to randomization may be re-screened for this study. The following assessments do not need to be repeated at the rescreen provided they still fall within the acceptable screening time window: TVU, endometrial biopsy, mammogram, ECG and Pap test (or equivalent cervical cytology). History of average caffeinated beverage intake will be collected at baseline. At each clinic visit, the caffeinated beverage intake within the past 24 hours will be recorded.
- b. The follow-up visit (visit 16) will occur approximately 3 weeks following the last dose of study drug.
- c. Subjects will return to the study site for visits and procedures to occur within ± 3 days of the scheduled day. Unscheduled visits can be planned outside the scheduled visits.
- d. Signed informed consent will be collected for all subjects before any study-related procedures are conducted.
- e. At screening, in the event that the subject does not have a documented normal/negative or no clinically significant findings mammogram from the previous 12 months on record. A mammogram at week 52/EOT/ED will be conducted if it coincides with the regularly scheduled routine screening mammogram of the patient, in accordance with local medical practice guidelines and the patient's primary care physician.
- f. Includes age, race, sex and smoking status (smoker/non-smoker), etc. Demographic information may vary based on country requirements.
- g. Includes height (at the screening visit only), weight and waist circumference. A bimanual clinical pelvic and clinical breast examination will be performed at the screening visit. A bimanual clinical pelvic examination can be performed at any time in the study where clinically indicated.

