- p. For practical reasons, the timing of DXA may vary from the actual time of the visit, depending on the DXA availability (DXA appointment). The screening visit (days -35 to -1 [visit 1]) DXA can be performed once the subject has been deemed eligible based on screening laboratory tests, or at visit 2 but must be performed before randomization. The week 52 (visit 15) DXA should be performed between week 50 and week 52, inclusive. For subjects who are withdrawn from the study prior to completion, a DXA will be completed as soon as possible after study drug discontinuation (preferably within 2 weeks).
- q. For HBsAG, anti-HCV antibodies, anti-HBs antibodies, anti-HBc antibodies and anti-HIV antibodies.
- r. Pharmacodynamic samples will be taken predose (1 hour) at day 1 (visit 2), week 4 (visit 3), week 12 (visit 5), week 24 (visit 8), at week 52 (visit 15) and week 55 (visit 16). Markers include LH, FSH, E2, SHBG, androstenedione, dehydroepiandrosterone, estrone and testosterone.
- s. Pharmacokinetic samples to be taken predose at week 4 (visit 3), week 12 (visit 5), week 24 (visit 8), and at EOT/ED week 52 (visit 15) and at 1 to 3 hour postdose at week 4 (visit 3). A predose sample will be collected for any subject with a signal of elevated ($> 3 \times$ ULN) transaminases. For the week 52 (visit 15) PK/PD samples, the last dose of study drug should be administered the day prior to the week 52 (visit 15) visit. Sites should collect week 52 (visit 15) PK/PD samples approximately at the same time when study drug would typically be given on site.
- t. A clinician will administer the C-SSRS measure electronically at the clinic visit, prior to any invasive procedures. This will be administered electronically via the site tablet at screening, (visit 1), week 0 (visit 2), week 12 (visit 5), week 24 (visit 8), EOT/ED week 52 (visit 15) and the follow-up visit (week 55 [visit 16]).

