5 TREATMENTS AND EVALUATION

5.1 Dosing and Administration of Study Drug(s) and Other Medication(s)

5.1.1 Dose/Dose Regimen and Administration Period

Subjects will be screening up to 35 days prior to randomization. Informed consent will be obtained prior to randomization and before any study-related procedures are performed.

Subjects will be assigned study drug as a kit containing either fezolinetant or placebo at visits indicated in the schedule of assessments. Study drug intake will be done with a glass of room temperature tap water in the morning. The first intake of study drug will take place at the study site on day 1 (visit 2) under the supervision of the study staff.

On study visit days (except for EOT/ED week 52 [visit 15]) study drug will be taken at the study site, under the supervision of the study staff, after collection of predose blood samples. On all other days throughout the treatment period, subjects will be instructed to take their dose of study drug at home with water, in the morning.

In the event of a missed dose, the subject should skip the missed dose and continue with the next scheduled dose.

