5.8 Adverse Events and Other Safety Aspects

5.8.1 Definition of Adverse Events

An AE is any untoward medical occurrence in a subject administered a study drug, and which does not necessarily have to have a causal relationship with this treatment. An AE can therefore be any unfavorable and unintended sign (including an abnormal laboratory finding), symptom, or disease (new or exacerbated) temporally associated with the use of a medicinal product whether or not considered related to the medicinal product.

In order to identify any events that may be associated with study procedures and could lead to a change in the conduct of the study, Astellas collects AEs even if the subject has not received study drug treatment. AE collection begins after the signing of the informed consent and will be collected until 21 days after the last dose of study drug or the subject is determined to be a screen failure.

Care will be taken not to introduce bias when detecting AEs and/or SAEs. Open-ended and non-leading verbal questioning of the subject is the preferred method to inquire about AE occurrences.

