5.8.5 Reporting of Serious Adverse Events (SAEs)

The collection of AEs and the expedited reporting of SAEs will start following receipt of the informed consent and will continue until 21 days after last administration of study drug or the subject is determined to be a screen failure.

In the case of a SAE, the investigator must contact the sponsor by fax or email immediately (within 24 hours of awareness).

The investigator must complete and submit an SAE worksheet containing all information that is required by local and/or regional regulations to the sponsor by email or fax immediately (within 24 hours of awareness).

The SAE worksheet must be signed by a medically qualified investigator (as identified on Delegation of Authority Log). Signature confirms accuracy and completeness of the SAE data as well as the investigator causality assessment including the explanation for the causality assessment.

If the SAE is associated with emergency unblinding as outlined in [Section 4.4.4 Breaking the Treatment Code for Emergency](#) this is to be recorded on the SAE worksheet. Within the SAE worksheet, the investigator is to include when unblinding took place in association with the SAE.

For contact details, see [[Section II Contact Details of Key Sponsor's Personnel](#)]. Fax or email the SAE/Special Situations Worksheet to:

Astellas Pharma Global Development Inc.
Pharmacovigilance
Fax number: (+1) [contact]
Alternate fax number: (+1) [contact]
Email: [contact]

If there are any questions, or if clarification is needed regarding the SAE, please contact the sponsor's medical monitor/study physician or his/her designee [[Section II Contact Details of Key Sponsor's Personnel](#)].

Follow-up information for the event should be sent promptly (within 7 days of the initial notification).

Full details of the SAE should be recorded on the medical records, SAE/Special Situation Worksheet and on the (e)CRF.

The following minimum information is required:

- International Study Number (ISN)/Study number,
- Subject number, sex and age,
- The date of report,
- A description of the SAE (event, seriousness criteria),
- Causal relationship to the study drug (including reason), and
- The drug provided (if any) <blinded regimen is also an option>

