7.6.1 Adverse Events

A TEAE is defined as an AE observed after starting administration of the study drug and 21 days after the last dose of study drug.

The number and percentage of subjects with treatment-emergent AEs, SAEs, AEs leading to withdrawal of treatment and AEs related to study drug will be summarized by SOC, preferred term and treatment group. The number and percentage of AEs by severity will also be summarized. All AEs will be listed.

A study drug-related TEAE is defined as any TEAE with a causal relationship of YES by the investigator.

AEs will be coded using MedDRA. An AE with onset at any time from first dosing until last scheduled procedure will be classified as treatment-emergent for inclusion in the summary tabulations.

An overview and separate summaries by SOC and preferred term of the number and percentage of subjects with TEAEs, drug-related TEAEs, TEAEs leading to withdrawal of treatment and TEAEs excluding SAEs and drug-related TEAEs leading to withdrawal of treatment will be presented by treatment group. Also included in the overview are the number and percentage of subjects with serious TEAEs, drug-related serious TEAEs, TEAEs leading to death, and drug-related TEAEs leading to death.

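### The adverse event period ends inconsistently and can close before a permitted follow-up visit, and an end-of-treatment visit on Day 351 loses its Week 52 laboratory and vital-sign values (minor)

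*SAP*

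**What the plan says.** **Last dose.** Protocol 5.1.1 removes the on-site dose at Visit 15: "On study visit days (except for EOT/ED week 52 [visit 15]) study drug will be taken at the study site". Table 1 footnote s adds that "the last dose of study drug should be administered the day prior to the week 52 (visit 15) visit".

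**Follow-up visit.** Table 1 and the design diagram in protocol 2.2.1 put Visit 16 on Day 386. Footnote c has visits take place "within ± 3 days of the scheduled day". Footnote b uses a different anchor: "The follow-up visit (visit 16) will occur approximately 3 weeks following the last dose of study drug".

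**End of the adverse event period.** Two rules stand side by side.
- 21 days: under protocol 5.8.1, adverse events "will be collected until 21 days after the last dose of study drug". Under 5.8.5, collection and expedited reporting "will continue until 21 days after last administration of study drug". The opening sentence of 7.6.1 uses the same limit for treatment-emergent events, and SAP 6.5.1 ends them "21 days after the last dose of study drug (when AE collection closes".
- Longer: protocol 7.6.1 also says "An AE with onset at any time from first dosing until last scheduled procedure will be classified as treatment-emergent". Table 1 footnote x monitors adverse events to the last study-related activity, and Table 1 schedules adverse event collection at Visit 16.

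**Week 52 windows.** Table 1 allows Visit 15 from 14 days before to 6 days after Day 365. In SAP 6.10.1, columns a) (laboratory and urinalysis) and b) (vital signs) define Week 48 as Days 324 to 351 and Week 52 as Days 352 to 376. If several values fall in one window, the one nearest the scheduled day is used.

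**The concern.** Frequency and severity of adverse events is a primary endpoint, and SAP 6.5.1 defines the events of special interest, including liver test elevations, among treatment-emergent events. The categorical liver table in SAP 6.5.2.1 stops one day after the last dose, so an off-drug transaminase rise is counted as an event mainly through the adverse event tables. An abnormality first detected at the follow-up visit would naturally take that day as its onset. If that day is past day 21, the SAP rule excludes it and the longer protocol rule includes it.

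The timing is not hypothetical. Protocol 1.5 reports that 2 of the 9 phase 2b transaminase cases arose during follow-up. Protocol 2.2.2 places one of them at the follow-up visit 3 weeks after the last dose, and records it as unlikely to be related to study drug.

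The second matter is smaller. A woman who completes treatment within the permitted window can have her end-of-treatment laboratory and vital-sign results left out of every by-visit summary because of a one-day mismatch between the protocol window and the SAP window.

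**Working it through.** **A. Adverse event period against the follow-up visit**

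Inputs: Visit 15 nominal Day 365, Visit 16 nominal Day 386, window ± 3 (Table 1); last dose the day before Visit 15 (footnote s); limit of 21 days after last dose (protocol 5.8.1 and 5.8.5, SAP 6.5.1).

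1. Visit days follow 7 × week + 1, so Week 52 is Day 365 and Week 55 is Day 386. The plan's 21 days is reproduced as 386 − 365 = 21, that is, with a last dose on Day 365.
2. With the stated dosing rule the last dose is on Day 365 − 1 = 364, and the 21-day period closes on Day 364 + 21 = 385.
3. A visit on Day 386 is 386 − 364 = 22 days after last dose.
4. Day 386 ± 3 is Days 383 to 389, or 19 to 25 days after last dose. Days 386 to 389 (22, 23, 24 and 25 days) are outside: 4 of 7.
5. Anchored on footnote b, the target is Day 364 + 21 = 385. Applying ± 3 to that anchor (an assumption) gives 18 to 24 days. Days 22, 23 and 24 are outside: 3 of 7.
6. The figure of 25 days is not a general maximum. If Visit 16 stays at Days 383 to 389 while Visit 15 moves within its own window:
   - Visit 15 on Day 351, last dose Day 350: 383 − 350 = 33 to 389 − 350 = 39 days.
   - Visit 15 on Day 371, last dose Day 370: 383 − 370 = 13 to 389 − 370 = 19 days.

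**B. Visit 15 on Day 351**

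1. The permitted days are 365 − 14 = 351 to 365 + 6 = 371, which is 21 days. Only Day 351 lies in the Week 48 window (324 to 351); Days 352 to 371 lie in Week 52.
2. Distance from the Week 48 target, Day 337: the Day 351 value is 351 − 337 = 14 days away; an in-window Visit 14 (Days 334 to 340) is at most 3 days away. The nearest-value rule takes Visit 14.
3. The last dose is on Day 350, and SAP 6.10.1 ends on-treatment windows one day after the last dose, on Day 351. No later value can fill Week 52, and Day 351 is too early for the Follow-up window, which starts at last dose + 2. The Day 351 value is therefore selected for no visit.
4. Without any closer Week 48 value, the Day 351 value is used as Week 48, and Week 52 is still empty.
5. Unaffected on Day 351:
   - Pharmacodynamic and pharmacokinetic samples, EQ-5D-5L, MENQOL and C-SSRS (Week 52 window 268 to 376), and ECG (2 to 376).
   - Ultrasound and DXA (Day 2 to last treatment + 30 days).
   - Biopsy (351 is after Day 326, SAP 6.5.5).
   - The highest-value liver table, which runs to last dose + 1 = Day 351, and the worst-finding shift tables.

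**The case against.** The strongest reply on the first part is that Day 386 is not the only definition of an on-schedule visit. Footnote b and the design sections count 3 weeks from the last dose, which gives Day 385, exactly 21 days and inside the limit. This stands: it would be wrong to infer that every on-schedule follow-up visit falls outside the adverse event period. It does not remove the problem, because the permitted spread around either anchor runs past day 21.

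A reader might also infer that whatever is found at a late Visit 16 is lost. The documents do not support that. Events are classified by onset, so one reported on Day 386 with onset by Day 385 still counts. Visit 16 laboratory, vital-sign and C-SSRS values are still summarised in the Follow-up window (SAP 6.5 and 6.10.1). Protocol 5.8.6 requires prompt notification of later events considered possibly related. What is lost is a tail of a few days of onsets, and only under the 21-day rule; the longer wording in protocol 7.6.1 would keep them. The defect is therefore an unreconciled definition.

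On the second part, it is tempting to say that the whole Day 351 visit is analysed as Week 48, or that about 5% of completers are affected (1/21). The first fails because only columns a) and b) are involved. The second needs end-of-treatment visits spread evenly over the window, which nothing in the documents supports.

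**Conclusion.** Both points hold, and both are minor.

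1. The documents give more than one end to the adverse event period, and the SAP adopts the shorter rule as being per protocol. Under that rule a permitted follow-up visit can fall after the period closes: 4 of 7 days if Visit 15 is on Day 365 and Visit 16 is anchored on Day 386, or 3 of 7 if it is anchored 3 weeks after last dose with ± 3 days (an assumption). The effect is confined to events with onset after day 21, which drop out of the treatment-emergent and special-interest counts. Their number cannot be derived from the documents.
2. One of 21 permitted end-of-treatment days leaves Week 52 empty in the by-visit laboratory, urinalysis and vital-sign summaries. How many women have their visit on Day 351 is unknown.

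**What to change.** **Adverse event period.** Reconcile protocol 5.8.1, 5.8.5, 7.6.1 and Table 1 footnote x with SAP 6.5.1, so that all state one end point that includes Visit 16. One workable form is the later of Visit 16 and 21 days after last dose. Do not add a 25-day cap, since that figure holds only for an end-of-treatment visit on Day 365. The cost is wording, as the visit and its adverse event collection are already scheduled. The downside is that a few more off-drug events are counted; it should not be assumed that these fall equally across arms.

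**Analysis windows.** In SAP 6.10.1, columns a) and b), set Week 48 to Days 324 to 350 and Week 52 to Days 351 to 376. An in-window Visit 14 (Days 334 to 340) stays in Week 48, so no scheduled visit is displaced.

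Both changes should be made before database lock and unblinding.
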